5.1 Measures Used

Measures may be completed using hard copies, online (REDCap), or by RA interview, depending on the respondent's preference and research restrictions due to COVID-19. During the COVID-19 open trial, any hard copies will be mailed, digital copies will be emailed and RA interviews will occur over the phone or other telehealth medium.

Sociodemographic Characteristics:

Demographics: Surrogate decision-makers' will be asked in a self-report assessment occurring either in clinic or over the telephone their own and the patient's age (years), gender, race, education, mental health history, income, marital status, religious/spiritual beliefs, ACP knowledge/understanding, treatment preferences, prognostic understanding, and relationship with patient. Stakeholders will report on their own demographics.

Medical factors for Patients:

Patients' diagnoses (e.g., Stage IV pancreatic or NSCL cancer), reason for hospital/ICU admission, DNR/DNI order status, ACP items (including palliative care consultations), care plans obtained from the medical chart or ICU physicians and fellows, as well as clinically relevant symptoms related to patient incapacity, such as but not limited to, delirium. This information will be compiled as a medical chart abstraction and matched with surrogate-assessed patient treatment preferences assessed at T1 to create a measure of rates of value-concordant care. These medical factors, in addition to the CEQUEL ²³, will serve to measure the outcomes specified in Aim #3.

Psychosocial factors for Surrogate decision-makers:

Screener: Consists of items from 4 items from McGill Quality of Life¹⁹, two items from the Partner Dependency Scale ¹⁸, and two items from the Columbia Suicide Severity Rating Scale ²⁰.

Adult Surrogate Pre-intervention/ Baseline Assessment (T1): Psychiatric History, Demographics, and Treatment Preferences; Prolonged Grief Disorder (PG-12) Caregiver Version; ²⁴ ^{25,26}; Fear of Losing Loved Ones Scale (FOLLOS); Peritraumatic Distress Inventory (PDI) ²⁷; Peritraumatic Dissociative Experiences Questionnaire (PDEQ) ICU Version²⁸; Impact of ICU Events Scale-Revised (IES-R) ²⁹; Brief Experiential Avoidance Questionnaire (BEAQ); ³⁰State Trait Anxiety Inventory - State scale (STAI) ³¹; Patient Health

Questionnaire (PHQ-9); ³² Distress Tolerance Scale (DTS) ³³ revised version; Caregiver Self-Efficacy in the ICU Scale; Decision Regret Scale (DRS) – EMPOWER³⁴; Regret Assessment.

Adult Surrogate Post-intervention Assessment (T2): PG-12 (if patient is alive); FOLLOS (if patient is alive); PG-13 (if patient is deceased); ²⁴ ^{25,26} PDI; PDEQ; IES-R; BEAQ; STAI; DTS revised version; Caregiver Self-Efficacy in the ICU Scale; DRS - EMPOWER; Regret Assessment; Post-Intervention Satisfaction Questionnaire (PISQ).

Adult Surrogate 1 Month Post-T2 Assessment (T3): PG-12 (if patient is alive); FOLLOS (if patient is alive); PG-13 (if patient is deceased); PDI; IES-R; BEAQ; STAI; PHQ-9; DTS revised version; Critical Care Family Satisfaction Survey- EMPOWER; CEQUEL-R (if patient is alive); CEQUEL ²³ (if patient is deceased); Quality of Life (if patient is alive); Quality of Death (if patient is deceased); DRS - EMPOWER; Regret Assessment; Medical Information Update

Adult Surrogate 3 Months Post-T2 Assessment (T4): PG-12 (if patient is alive); FOLLOS (if patient is alive); PG-13 (if patient is deceased); PDI; IES-R; BEAQ; STAI; PHQ-9; DTS revised version; CEQUEL-R (if patient is alive); CEQUEL (if patient is now deceased, but was alive at T3); Quality of Life (if patient is alive); Quality of Death (if patient is deceased); DRS - EMPOWER; Regret Assessment; Medical Information Update; Qualitative Exit Interview for (participants receiving EMPOWER intervention only).

Pediatric Surrogate Assessments: STAI, PDI, PG-12, IES-R, DRS-EMPOWER at all 4 timepoints, with brief demographics at T1, Post-Intervention Satisfaction Questionnaire at T2, and Qualitative Exit Interview at T4 (for participants receiving EMPOWER intervention only).

Measure Title	Time Points Used*	Description of Measure
McGill Quality of Life Scale	Screener	Items 5 through 8 are used to measure anxiety/depression.
Partner Dependency Scale (PDS)	Screener	Items 1 and 2 of the PDS are used to measure dependency. The language is altered to refer to the patient rather than a spouse.
Columbia Suicide Severity Rating Scale	Screener	Items 1 and 2 of the CSSRS are used to measure suicidal ideation.
Peritraumatic Distress Inventory (PDI) ICU Version	T1, T2, T3, T4	Measures peritraumatic distress.
Peritraumatic Dissociative Experiences Questionnaire (PDEQ) ICU Version	T1, T2	Measures experiences of dissociation that may occur in the ICU. Instructions are changed to prompt the participant to specifically answer the survey in reference to their experience in the ICU.
Impact of ICU Events Scale- Revised (IES-R)	T1, T2, T3, T4	Measures symptoms of PTSD.
Brief Experiential Avoidance Questionnaire (BEAQ)	T1, T2, T3, T4	Measures experiential avoidance.
State Trait Anxiety Inventory (STAI) - State	T1,.T2, T3, T4	Measures symptoms of generalized anxiety disorder.
Patient Health Questionnaire (PHQ-9)	T1, T3, T4	Measures symptoms of depression.
Distress Tolerance Scale (DTS)	T1, T2, T3, T4	Measures ability to tolerate distress. Items 1, 2, 9, and 13 are retained from the original.
Decision Regret Scale (DRS) – EMPOWER	T1, T2, T3, T4	Measures symptoms of decision regret. Modifies instructs of original instrument to include a specific indexed regret.
Regret Assessment	T1, T2, T3, T4	Measures distress or remorse after a health care decision made by the participant. Items were developed by clinicians and an expert in psychometrics to identify common difficulties faced by caregivers in the ICU setting.
Caregiver Self-Efficacy in the ICU Scale	T1, T2	Items were developed by clinicians and an expert in psychometrics to identify common difficulties faced by caregivers in the ICU setting.
Critical Care Family Satisfaction Survey - EMPOWER	Т3	Measures caregiver's reported feelings towards the medical team and regarding medical decisions in the ICU. Items were developed by clinicians and an expert in psychometrics to tailor the instrument to the ICU setting based on a scale created by Wasser & Matchet ³⁵ .

Post-Intervention Satisfaction Questionnaire	T2	Measures satisfaction with EMPOWER intervention or usual care, as well as acceptability, feasibility, and tolerance. Items were developed by clinicians and an expert in psychometrics. Items measuring acceptability were developed based on an empirically- validated framework of healthcare intervention acceptability that measures constructs of participant affect, burden, intervention coherence, opportunity costs, perceived effectiveness, and self-
Enhanced Usual Care Tracker	T2 (for Enhanced Usual Care group only)	Measures utilization of Enhanced Usual Care resources.
Prolonged Grief Disorder (PG-12) Caregiver Version	T1, Status dependent @ T2, T3, T4	Measures anticipatory grief. Language is changed to reflect that the patient has not died yet, and does not contain the duration criterion of 6 months as in PG-13.
Prolonged Grief Disorder (PG-13)	Status dependent @ T2, T3, T4	Measures grief.
Fears of Losing Loved Ones Scale (FOLLOS)	T1, Status dependent @ T2, T3, T4	Measures attachment-related distress associated with anticipatory grief. Items were developed by clinicians and an expert in psychometrics.
Caregiver Evaluation of the Quality of End-of-Life Scale (CEQUEL)	Status dependent @ T3, T4	Measures caregiver's subjective evaluation of the patient's quality of death. If administered at T3 due to patient death, will not be administered at T4.
CEQUEL-Revised	Status dependent @ T3, T4	Administered to caregivers whose patients are still living. Retains items measuring caregiver satisfaction with medical care for the patient, but removes questions regarding patient's death.
CEQUEL-Revised	Status dependent @ T3, T4	Administered to caregivers whose patients are still living. Retains items measuring caregiver satisfaction with medical care for the patient, but removes questions regarding patient's death.
Quality of Life/Death	Status dependent @ T3, T4	Measures caregiver's perception of the patient's most recent week of life (either their most recent week, or most recent week before death). If Quality of Death is administered at T3, it will not be administered again at T4. Items have been previously published upon and validated ² .

^{*}Refers to assessments for adult surrogate participants

Qualitative data:

All surrogate decision-makers will provide feedback on the intervention in a post-intervention satisfaction questionnaire at T2. Those assigned to the EMPOWER intervention will also participate in a qualitative exit interview at T4. Stakeholders will provide feedback on the intervention manual in self-report questionnaires, written form, and/or in-person interviews. Clinicians will provide information about the patient before recruitment occurs via the patient information form or discussion with research assistants.

5.2 Data Collection (Please find the details on data to be collected in 5.2)

Note: All patient and surrogate decision-maker identifiable information will be kept in a password protected electronic database, REDCap. Self-report data will be entered into and stored on the WCM REDCap server. Audio and video recorded data collected at all study sites will be stored on WCM's secure server. Research study staff at MSK will be given access to the data. Collected data will only be identified via a study ID that will serve as a link to identifiable information. Hard copies of the collected data will be kept in a locked file cabinet within a locked office and will only be accessible to the study PI and relevant study staff.

Confidentiality will be ensured by removal of identifying information (name, age, gender, race/ethnicity,) of the patients and surrogate decision-makers and substituting their names with study participant numbers. As noted, all data will be de-identified. Nonetheless, we will maintain a file that links subject name with the study ID thereby enabling us to locate the study participant's research record upon request. This file will also be utilized by study staff in order to repeatedly interact with participants actively enrolled in the study. Data will be analyzed in aggregate only, and no identities will be revealed. For any qualitative data or vignettes presented at conferences, in publications, or incorporated into the EMPOWER manual or materials, pseudonyms will be created for participants.

Data collected will be obtained by trained research staff who have experience interviewing study participants. The data will be used specifically for the purposes outlined in this proposal and not for any other purpose. All study related documents will be stored in a secure location until the study has ended and all data analyses are complete. At that time, all study material will be placed in a secured long-term storage facility until it is deemed appropriate to destroy the study material.

To reduce missing data, following completion of all assessments, study staff will review the contents of the measures and scan them for missing information. If missing information is found, the staff member will contact the subject or review the medical chart to fill in missing data. In these circumstances, a research assistant will reach out by phone to the participant up to two times, and subjects may decline to provide any missing data.

Staff at WCM, MSK, and NYPQ have extensive experience interviewing health professionals in a hospital setting. All are seasoned interviewers and trainers with considerable experience interviewing diverse study subjects. Training consists of learning the instruments, practice sessions, and instruction in administration of the research interviews, including IRB approved procedures for approaching and consenting potential study participants.

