6.1 Data Analysis Plan

Below are descriptions of the statistical procedures performed to test each of the hypotheses. Participant data will be stored in a locked file cabinet and using a secured REDCap database. Missing data will be estimated using a multiple imputation procedure described by Schafer and Olsen³⁷. There will not be a data monitoring committee due to the trial's relatively short duration and the minimal risks the intervention poses. Trial data will

not be independently audited. An interim analysis of the pilot data will occur to inform the conduct of the randomized control and edits to the EMPOWER manual. Data for participants who come bereaved before the administration of EMPOWER or EUC interventions will be treated as exploratory and analyzed separately.

Specific Aim #1: Develop EMPOWER for surrogate decision-makers of critically ill patients who at risk of becoming unable to communicate and/or are currently are unable to communicate in the ICU.

There are no hypotheses for this aim. We will use thematic content analysis, a well-established, systematic qualitative analysis approach in health research, to identify themes from stakeholder participants' narratives and exit interviews. We will follow Morse's²¹ guidelines for conducting rigorous qualitative research (e.g., audit trail, saturation) using Atlas.ti software. We will independently review each interview transcript as well as qualitative data gathered from manual edits and Delphi survey responses and will synthesize and interpret participants' feedback about the content of the EMPOWER manual.

Specific Aim #2: Determine the feasibility, tolerability, acceptability, and preliminary effects of EMPOWER on surrogate decision-maker mental health.

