We will compute descriptive statistics to characterize the feasibility and acceptability of EMPOWER by examining helpfulness/satisfaction ratings, rates of recruitment, reasons for refusal, and number of modules/booster calls completed. Targets will include completion of 4/6 modules for feasibility and tolerability. Target acceptability will be an average score greater than 3 on the acceptability items in the post-intervention satisfaction questionnaire among participants who received EMPOWER. Tolerability will also be measured by open ended-responses to qualitative questions asked at T4 regarding negative experiences, emotional difficulties, and perceived costs and benefits of participating in the intervention. Drop-out will not be considered as a metric of tolerability due to the highly stressful and variable circumstances of ICU caregiving, unless participants drop out of the study and specifically express that they consider it to be too distressing. Qualitative data analysis will be used to analyze data from open-ended questions to identify the most helpful components of EMPOWER.

To evaluate the preliminary effects of EMPOWER among participants in the combined RCT and COVID-19 open trial phases, we will use a hierarchical linear modeling (HLM) and an intent-to-treat approach. HLM is statistically appropriate because of the clustering within interventionists and within surrogate decision-makers. HLM will correct for this clustering by modeling interventionists and surrogate decision-makers as random effects, as has been done in prior trials ^{38 39}. This will also provide a treatment assignment model coefficient and effect size estimate for our future, larger study.

HLM modeling will determine differences between surrogate decision-makers and patients assigned to EMPOWER vs. enhanced usual care. The primary outcome is post-intervention (T2) differences in PDI scores. Secondary outcomes are differences in scores on the PGD 12/13 and BEAQ at one-month (T3) and three-month (T4) follow up from T2. Exploratory outcomes are differences in scores on the IES-R, STAI, PHQ-9 and Decision Regret Scale at one-month (T3) and three-month (T4) follow up. HLM models will include covariates, either as fixed-effect or time-varying, if those variables are found to be significantly statistically associated with both intervention assignment and the outcome examined.

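### The paediatric battery omits BEAQ and PHQ-9 and names no post-loss grief scale, so these outcomes cannot be analysed in the combined sample as the plan states

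*Combined protocol and SAP*

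**What the plan says.** Section 3.1 Eligibility Criteria admits surrogates of patients under 18 to both the RCT and the COVID-19 open trial. Section 5.1 Measures Used gives them their own battery: "Pediatric Surrogate Assessments: STAI, PDI, PG-12, IES-R, DRS-EMPOWER at all 4 timepoints". Brief demographics, a satisfaction questionnaire and, for EMPOWER recipients, an exit interview complete it.

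Surrogates of adult patients also receive BEAQ at every visit and PHQ-9 at T1, T3 and T4. From T2 onward their grief scale follows the patient's status: PG-12 if alive, PG-13 if deceased. The measures table describes PG-12 thus: "Language is changed to reflect that the patient has not died yet". A footnote limits that table's time points to surrogates of adult patients.

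Section 6.1 Data Analysis Plan estimates effects "among participants in the combined RCT and COVID-19 open trial phases" by intent-to-treat. It makes PDI at T2 primary. The next tier reads: "Secondary outcomes are differences in scores on the PGD 12/13 and BEAQ", both assessed at T3 and T4. PHQ-9 belongs to a third, exploratory tier, together with the Decision Regret Scale, STAI and IES-R. For incomplete data the section has one rule: "Missing data will be estimated using a multiple imputation procedure".

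**The concern.** The outcome list and the paediatric instrument list do not match, and nothing in the plan restricts any outcome to surrogates of adult patients. This leaves two gaps.

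The first is BEAQ. The Introduction says EMPOWER is designed to reduce experiential avoidance, so BEAQ measures the intervention's stated target. Section 6.1 also says the model is to supply an effect size for the larger trial. If the plan is followed as written, that estimate either includes imputed values for a whole subgroup that was never asked the questions, or comes from a narrower population than the one named. PHQ-9 has the same problem at exploratory level.

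The second is grief. Section 5.2 Study Design defines this outcome as pre-loss or post-loss grief, whichever applies. For a paediatric surrogate whose child dies during follow-up, no post-loss instrument is listed.

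**Working it through.** **1. Outcomes set against the paediatric battery (sections 6.1 and 5.1)**

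| Outcome | Level | Collected from paediatric surrogates? |
|---|---|---|
| PDI at T2 | Primary | Yes |
| BEAQ at T3, T4 | Secondary | No, at no visit |
| PGD 12/13 at T3, T4 | Secondary | PG-12 only; no PG-13 listed |
| PHQ-9 at T3, T4 | Exploratory | No, at no visit |
| IES-R, STAI, Decision Regret Scale | Exploratory | Yes |

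**2. Who is affected on grief.** PG-12 is a usable measure while the child lives. Section 6.1 sets aside, as a separate exploratory analysis, anyone bereaved before EMPOWER or enhanced usual care is given. The gap is therefore confined to paediatric surrogates bereaved after that point and before T3 or T4. The documents give no count.

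**3. What literal imputation would do.** BEAQ is absent at baseline as well as follow-up, so no paediatric record has an observed value to anchor it. Its relation to the shared instruments (PDI, STAI, PG-12, IES-R, DRS) could be estimated only in surrogates of adult patients and then carried over. The data cannot test that transfer. The groups also enter differently: sections 3.1 and 5.3.1 screen surrogates of adult patients for dependency and anxiety (or accept them on a clinician's report of distress), whereas paediatric surrogates are screened only for suicidal ideation.

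**4. Illustration of the alternative, no imputation.** The plan's only power figure for the combined sample (Statistical power and sample size considerations) is 80% at d = 0.75, alpha 0.05, with 40:20. Two-sided testing is assumed. The noncentrality is λ = d / √(1/n₁ + 1/n₂) = 0.75 / √(1/40 + 1/20) = 2.74. The normal approximation gives Φ(2.74 − 1.96) = 78.2%, which is close to the stated figure; the noncentral t gives 76.8%.

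Let f be the paediatric fraction, equal in both arms. Then n₁ = 40(1 − f) and n₂ = 20(1 − f). Both f and its balance across arms are assumptions.

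| f | BEAQ sample | Power at d = 0.75 (t) | d detectable at 80% power |
|---|---|---|---|
| 0 | 60 (40:20) | 76.8% | 0.78 |
| 0.1 | 54 (36:18) | 72.2% | 0.82 |
| 0.2 | 48 (32:16) | 66.9% | 0.88 |
| 0.3 | 42 (28:14) | 60.9% | 0.94 |

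Only the change down the rows belongs to this point. The difference between 80% and 76.8% does not. The plan does not tie d = 0.75 to BEAQ, and clustering and drop-out are ignored here. Steps 3 and 4 are alternatives: values are imputed and the nominal n stays at 60, or they are not and n falls.

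**The case against.** The strongest reply concerns grief. Section 5.3.1 says in general terms that measures depend on the patient's status. Where the record does not show that status, participants are contacted a week ahead so that the right questionnaires are given. This is not limited to surrogates of adult patients, and it follows the paediatric procedure in the same section. A reader might infer from the unconditional paediatric list that bereaved parents will be asked about a living child; no section says so, and section 5.3.1 points the other way. It does not close the gap, however. It refers on to detailed rules, and the only detailed rules are the lists for surrogates of adult patients and a table footnoted to them. The paediatric post-loss scale remains unspecified.

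On imputation, section 5.2 Data Collection treats missing data as blanks in completed assessments that staff then chase. Nothing says that instruments left out by design will be imputed, so a reader should not take that as the sponsor's intention. But the imputation sentence has no limit, and it is the plan's only rule for analysing incomplete data.

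The short battery is also deliberate: section 5.3.1 calls the paediatric T1 assessment brief and PICU-specific. That is a fair reason not to lengthen it, but it does not reconcile the battery with the outcome list. Finally, power for a secondary outcome is not decisive in a pilot meant to give preliminary effect sizes. That stands, and the point does not rest on power.

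**Conclusion.** The point holds in limited form. BEAQ (secondary) and PHQ-9 (exploratory) cannot be analysed by intent-to-treat in the combined sample as stated, because a group eligible for that sample never receives them. The grief outcome lacks a specified instrument for paediatric surrogates bereaved after the intervention starts and before T3 or T4.

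It would be tempting to conclude that neither secondary outcome can be analysed. The documents do not support that: PG-12 is valid for parents of living children, and most of the grief analysis may be untouched. The primary outcome is not touched at all.

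The size cannot be fixed from the documents, which give neither the paediatric share nor the number bereaved during follow-up. The sample sizes and power above illustrate an assumed range and are not a measured loss. The omission of BEAQ and PHQ-9 is read directly from the lists. The grief gap rests on reading section 5.3.1 as supplying no paediatric rule.

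**What to change.** 1. In section 5.1 Measures Used, make the paediatric grief measure depend on the child's status, as for adults: PG-12 if the child is alive, PG-13 if deceased. In section 6.1, score both on their shared symptom items so that they can enter one PGD 12/13 model. The measures table says PG-12 is reworded and lacks PG-13's six-month duration criterion. The documents do not reproduce the items, so the shared set must be confirmed from the forms.

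2. In section 6.1 Data Analysis Plan, restrict the BEAQ and PHQ-9 analyses to surrogates of adult patients, exclude instruments not administered by design from multiple imputation, and report the n contributing to each outcome.

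The cost is small. PG-13 and the rule for choosing it already exist in the study, and the rest is analysis wording. The downside is a smaller stated sample for BEAQ and PHQ-9, and no estimate of either effect in paediatric surrogates. Adding BEAQ to the paediatric battery for remaining enrolment would partly avoid this, but it trades against the intended brevity and is a choice for the sponsor, not a needed correction.
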